### 9.7. Data Analysis

Detailed methodology for summary and statistical analyses of data collected in this study will also be documented in a statistical analysis plan (SAP), which will be dated, filed and maintained by the sponsor. *[The SAP may modify the plans outlined in the protocol; any major modifications of primary endpoint definitions or their analyses would be reflected in a protocol amendment].*

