#### **9.7.6. Methods Under Objective 4**

*Objective 4: To evaluate tumor response among AML patients who received Mylotarg in a real-world setting.*

- a. First and best tumor response in the first qualifying Mylotarg-containing R/R-based line of therapy.
- b. Time to best response in the first qualifying Mylotarg-containing R/R-based line of therapy.
- c. Duration of best response in the first qualifying Mylotarg-containing R/R-based line of therapy.

Tumor response will be assessed for the first and best overall response to treatment for the first qualifying Mylotarg-containing R/R-based line of therapy during the study period. Response classifications will be made based on the treating physician's documentation of response itself, typically informed by radiological scan reports noted in the patient record. Classification is made to the following categories: complete response, partial response (PR), stable disease (SD), progressive disease (PD), and not evaluable (NE), each based on the treating physician's statements. In cases where complete response with partial hematologic recovery (CRh), complete response with incomplete hematologic recovery (CRi), and morphologic leukemia-free state (MLFS) are explicitly included in the treating physician's statements, these additional classifications will be documented. Patients for whom the record did not clearly indicate one of these classifications will be classed as NE. These patient responses will also be classified under a secondary classification as Other Favorable, or Other Unfavorable, where the record indicated the general direction of effect in order to preserve response information for each patient, even when not classifiable according to standard response categories; these responses can be assessed in descriptive analysis. The date of the best overall response for the first qualifying Mylotarg-containing R/R-based line of therapy will be collected from the index date through the end of the third R/R-based line of therapy or the end of record, whichever occurs first. Tumor responses captured are based on treating physician's assessment in the medical record. Overall response rate will be defined as a percentage of patients whose best response is either CR, CRi or MLFS, where available. Time to best response and duration of best response will be assessed using the descriptive techniques described above.

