## **10.3. Institutional Review Board (IRB)/Independent Ethics Committee (IEC)**

There must be prospective approval of the study protocol, protocol amendments, and other relevant documents (eg, informed consent forms if applicable) from the relevant IRBs/IECs. All correspondence with the IRB/IEC must be retained. Copies of IRB/IEC approvals must be forwarded to Pfizer.

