## **12. PLANS FOR DISSEMINATING AND COMMUNICATING STUDY RESULTS**

The final study report will be completed by Concerto HealthAI and is estimated to be available in July 2020.

In the event of any prohibition or restriction imposed (eg, clinical hold) by an applicable competent authority in any area of the world, or if Concerto HealthAI is aware of any new information which might influence the evaluation of the benefits and risks of a Pfizer product, Pfizer should be informed immediately.

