## REVISION HISTORY

SAP Version 1.0 (April 1, 2020)

SAP Version 2.0 (September 9, 2020)

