## 4. STATISTICAL METHODS

### 4.1. Endpoints

The primary study endpoints are effectiveness outcomes of rwEFS/rwRFS, rwOS, and response. Patient demographics and clinical characteristics, as well as treatment patterns will also be evaluated.

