Response will be assessed for the first and best overall response to treatment for each regimen in the first qualifying Mylotarg-containing R/R-based line of therapy during the study period. Response classifications will be made based on the treating physician's documentation of response itself, typically informed by radiological scan reports noted in the patient record. Classification is made to the following categories: complete response (CR), partial response (PR), stable disease (SD), progressive disease (PD), and not evaluable (NE), each based on the treating physician's statements. In cases where complete response with partial hematologic recovery (CRh), complete response with incomplete hematologic recovery (CRi), and morphologic leukemia-free state (MLFS) are explicitly included in the treating physician's statements, these additional classifications will be documented. The date of the best overall response for each regimen in the first qualifying Mylotarg-containing R/R-based line of therapy will be collected. Responses captured are based on treating physician's assessment in the medical record. Overall response rate will be defined as a percentage of patients whose best response is either CR, CRi, or MLFS, where available. Time to best response and duration of best response will be assessed using the descriptive techniques described above.

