**Figure 3. Kaplan-Meier Analysis of rwOS from Start of First Mylotarg-Containing Line of Therapy, All Patients**

#### 7.4. Objective 4: Response

**Table 9. First Positive Response (First Mylotarg-Containing Line of Therapy), All Patients**

Description	L1 n=xxx	L2 n= xxx	L3 n=xxx
First Positive Response*, n (%)			
Complete Response (CR)	n (x.x%)	n (x.x%)	n (x.x%)
Partial Response (PR)	n (x.x%)	n (x.x%)	n (x.x%)
Stable Disease (SD)	n (x.x%)	n (x.x%)	n (x.x%)
Progressive Disease (PD)	n (x.x%)	n (x.x%)	n (x.x%)
Not Evaluable (NE)/Undocumented	n (x.x%)	n (x.x%)	n (x.x%)
Other Favorable	n (x.x%)	n (x.x%)	n (x.x%)
Other Unfavorable	n (x.x%)	n (x.x%)	n (x.x%)
Complete Response with Partial Hematologic Recovery (CRh) ±	n (x.x%)	n (x.x%)	n (x.x%)
Complete Response with Incomplete Hematologic Recovery (CRi) ±	n (x.x%)	n (x.x%)	n (x.x%)
Morphologic Leukemia-Free State (MLFS) ±	n (x.x%)	n (x.x%)	n (x.x%)
Overall Response Rate**±	xx (xx.x%)	xx (xx.x%)	xx (xx.x%)

\* Responses are based on treating physician's assessment as provided in the medical records.

\*\* Overall response rate is defined as a percentage of patients whose best response is either CR, CRh or CRi.

± Based on provider documentation, which may result in low sample size of patients with certain response categories.

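### Overall response rate has two numerators: CR/CRi/MLFS in the SAP and protocol text, CR/CRh/CRi in the footnotes of all four SAP tables that report it

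*SAP*

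**What the plan says.** The methods text of the two documents agrees. SAP section 4.3.6: "Overall response rate will be defined as a percentage of patients whose best response is either CR, CRi, or MLFS, where available". Protocol section 9.7.6: "Overall response rate will be defined as a percentage of patients whose best response is either CR, CRi or MLFS, where available". Both count CR, CRi and MLFS, and neither counts CRh.

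Four SAP table shells carry an ORR row: Tables 9 and 10 (all patients) and Tables 14 and 15 (the ad hoc subset of section 4.3.7). Each has the same footnote: "Overall response rate is defined as a percentage of patients whose best response is either CR, CRh or CRi". That version counts CRh and leaves out MLFS. All four shells list CR, CRh, CRi and MLFS on separate rows and split the results into L1, L2 and L3 columns.

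On the standing of the endpoint, SAP section 4.1 says: "The primary study endpoints are effectiveness outcomes of rwEFS/rwRFS, rwOS, and response". On changes, protocol section 9.7 allows the SAP to depart from the protocol but adds that "any major modifications of primary endpoint definitions or their analyses would be reflected in a protocol amendment". Protocol section 5 records no amendments.

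**The concern.** The SAP contradicts itself on who counts as a responder. A patient whose best response is CRh is a non-responder under section 4.3.6 and a responder under the footnotes. A patient whose best response is MLFS is the reverse. This is more than a wording variant, because CRh and MLFS are recorded and tabulated as distinct categories. Every table that will display the rate departs from the methods section that defines it.

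The rate summarises an endpoint that the SAP calls primary, in a study of 20 to 30 patients, so one or two reclassified patients are visible in the percentage. If the choice is left open, it can be made after the counts are known, and the report could not show that it was not.

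A smaller point belongs with it. Tables 9 and 14 tabulate first positive response, yet the footnote to their ORR row refers to best response.

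**Working it through.** The plan gives no power, precision or expected ORR figure to reproduce. The check is a comparison of definitions followed by simple arithmetic.

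**1. Definitions side by side**

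| Place | CR | CRh | CRi | MLFS |
|---|---|---|---|---|
| SAP 4.3.6 | counted | no | counted | counted |
| Protocol 9.7.6 | counted | no | counted | counted |
| SAP Tables 9, 10, 14, 15 (footnotes) | counted | counted | counted | no |

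**2. Is there a rule that decides?** The only candidate is the clause in protocol section 9.7. It relates the SAP to the protocol and does not rank SAP text against SAP footnotes. The SAP text matches the unamended protocol, so nothing shows that the footnotes were a deliberate change.

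**3. Size of the difference.** Assume each patient is counted in exactly one response row:

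- Text rate = (CR + CRi + MLFS)/N
- Footnote rate = (CR + CRh + CRi)/N
- Text minus footnote = (MLFS − CRh)/N

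The input N = 20 to 30 comes from protocol section 9.5 and SAP section 3.3; 25 is the midpoint. The documents give no expected CRh or MLFS counts, so a net difference of 0 to 2 patients is an assumption.

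| N | Net 0 | Net 1 | Net 2 |
|---|---|---|---|
| 20 | 0 | 1/20 = 5.0 points | 2/20 = 10.0 points |
| 25 | 0 | 1/25 = 4.0 points | 2/25 = 8.0 points |
| 30 | 0 | 1/30 = 3.3 points | 2/30 = 6.7 points |

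**4. Planned cells.** No shell has an all-patient ORR column, so step 3 describes the whole cohort rather than a planned cell. The documents do not give the split by line. Assuming 5, 10 or 15 patients in a column, one net patient is 1/5 = 20.0, 1/10 = 10.0 or 1/15 = 6.7 points. Tables 14 and 15 cover a subset of unstated size.

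**5. Illustration with assumed counts** (N = 25, CR = 10, CRi = 2):

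- CRh = 1, MLFS = 1: text (10 + 2 + 1)/25 = 52.0%; footnote (10 + 1 + 2)/25 = 52.0%. The rates agree, although they count different patients.
- CRh = 2, MLFS = 0: text (10 + 2 + 0)/25 = 48.0%; footnote (10 + 2 + 2)/25 = 56.0%.

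**6. Dependence on the one-row assumption.** SAP section 4.3.6 first assigns CR, PR, SD, PD or NE and treats CRh, CRi and MLFS as further labels recorded when the physician states them. If a CRh patient also sits in the CR row, the text numerator already includes that patient and the CRh part of the gap disappears. The SAP does not say whether rows are exclusive.

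**The case against.** The case for giving this little weight has several parts.

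- **Endpoint status.** SAP section 4.1 names response, not ORR, and Objective 4 lists first and best response, time to best response and duration of best response. This stands as a matter of wording. Still, ORR is the only summary rate defined for response, and it has its own row in every table of response categories.
- **The footnotes look like the outlier.** The SAP text agrees with a protocol that has no amendments, which suggests an editorial slip. That is a fair inference and it supports the simplest repair. It is not a rule, because the protocol also allows the SAP to modify it.
- **Small practical effect.** No statistical comparison is planned. The table footnotes already warn that some response categories may have few patients, and separate rows let a reader recompute either rate. This largely stands, and it keeps the point modest. Recomputation works only if rows are exclusive, and not where the rate is quoted without its table.
- **All-patient percentages match no planned cell.** This is correct. They give the scale for the cohort, while the per-column figures rest on assumed sizes.
- **Tables 9 and 14.** A best-response rate under a first-response table repeats Tables 10 and 15 and can be called redundant rather than wrong. That is reasonable, and it favours deleting the row over inventing a new measure.

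**Conclusion.** The concern holds. The current SAP has two incompatible ORR numerators, one in the methods text (shared with the protocol) and one in all four reporting tables, and no stated precedence.

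With exclusive rows, the rates differ by (MLFS − CRh)/N. For an assumed net difference of 0 to 2 patients, that is 0 to 10.0 points at N = 20 and 0 to 6.7 points at N = 30. Shifts are larger in the line-of-therapy columns if those hold the assumed 5 to 15 patients. The direction depends on which category is more frequent, and the documents do not allow that to be predicted.

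No test or decision rule depends on ORR, so this should be fixed but does not undermine the study. That the contradiction exists is certain; how much it changes the reported rate is not known.

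**What to change.** Choose one numerator and use it in SAP section 4.3.6, protocol section 9.7.6 and the footnotes of Tables 9, 10, 14 and 15.

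- **Smallest change:** edit the four footnotes to match the existing text (CR, CRi, MLFS). This is one SAP revision. The protocol is untouched and no new data are needed, because CRh, CRi and MLFS are already to be recorded where stated.
- **Alternative:** adopt CR, CRh and CRi. This also changes protocol section 9.7.6. It may call for an amendment under protocol section 9.7 and then approval under section 10.3: "There must be prospective approval of the study protocol, protocol amendments".

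In the same revision:

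- State in section 4.3.6 that each patient is counted in one response row only.
- In Tables 9 and 14, delete the ORR row or define it explicitly on first response. Deletion is simpler, since Tables 10 and 15 carry the best-response rate.
- Optionally, show the rate under the other numerator as a supportive line in Tables 10 and 15.

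Make the choice before response counts are seen, if that is still possible. SAP version 2.0 is dated 9 September 2020, whereas protocol section 12 says the final report "is estimated to be available in July 2020". These dates do not prove that the counts were known. If they were, the report should say so and show both rates side by side.

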#### 4.3.7. Ad-Hoc Analyses

Ad-hoc analyses will be performed on a subset of patients assumed to be de-novo AML patients using a closer-to-typical combination of gemtuzumab + chemotherapy in 1L. This will include patients receiving idarubicin instead of daunorubicin, despite only daunorubicin being included in gemtuzumab's label. rwEFS FPR, and BOR will be evaluated among this subset of patients.

#### 4.4. Missing Data

This study reflects real-world patients treated primarily in the community oncology setting. The completeness of each patient’s medical chart will vary due to the nature of real-world data. Although some measurements may not be consistently available from patient records in the Definitive Oncology Dataset, analyses will be conducted based on data that are reported. Variables related to patient characteristics and certain treatment outcomes largely missing from the structured fields can be abstracted from the unstructured data. Based on prior studies conducted using Concerto data, the majority of the variables are estimated to be available for >90% of patients. The estimates can vary slightly based on different variables in different tumor types. For example, ELN classification of AML risk according to provider documentation may be limited. In general, data that are absent/not found will not be imputed but will be categorized and reported as not documented.

#### 5. LIMITATIONS

1. This study reflects treatment practice patterns only within the United States who are part of the Definitive Oncology Dataset. The majority of the data reflects treatment in community oncology settings (80%). It is possible that treatment patterns may differ in academic centers compared with community settings.
2. This study is retrospective. With the advent of newer therapies in AML, it is expected that treatment patterns will change during the next few years, and therefore, this study may not be reflective of future AML treatment patterns.
3. This study reflects a convenience sample of patients. It is possible that patients within the Definitive Oncology Dataset differ from the underlying AML population in ways that may not be measurable.
4. Some measurements may not be consistently available from patient records in the Definitive Oncology Dataset.

## 7. TABLE SHELLS

### 7.1. Objective 1: Demographic and Clinical Characteristics

#### 7.1.1. Demographic characteristics

**Table 1. Demographic Characteristics**

	N=xxx
Year of initial AML Diagnosis (n, %)	
2012	n (x.x%)
2013	n (x.x%)
2014	n (x.x%)
2015	n (x.x%)
2016	n (x.x%)
2017	n (x.x%)
2018	n (x.x%)
2019	n (x.x%)
Age (years) at initial AML Diagnosis	
n	xx
Mean	x.x
SD	x.x
1 st Quartile	x.x
Median	x.x
3 rd Quartile	x.x
IQR	x.x
Min, Max	x.x,x.x
Undocumented Age	xx
Age (years) at initial AML Diagnosis	
Sub-total	n (x.x%)
<65	n (x.x%)
≥65 -74	n (x.x%)
≥65	n (x.x%)
≥75	n (x.x%)
Undocumented Age	n (x.x%)
Gender n (%)	
Sub-total	n (x.x%)
Female	xx
Male	xx
Undocumented Gender	xx
Race, n (%)	
Sub-total	n (x.x%)
White	n (x.x%)
Black or African American	n (x.x%)
Other/Undocumented Race	n (x.x%)
Weight (pounds) at initial AML Diagnosis	
n	xx
Mean	x.x
SD	x.x

**Table 1. Demographic Characteristics**

	N=xxx
1 st Quartile	x.x
Median	xx
3 rd Quartile	x.x
IQR	x.x
Min, Max	x.x,x.x
Undocumented Weight	xx
Height (inches)	
n	xx
Mean	x.x
SD	x.x
1 st Quartile	x.x
Median	xx
3 rd Quartile	x.x
IQR	x.x
Min, Max	x.x,x.x
Undocumented Height	xx
BMI (kg/meters) at Initial AML Diagnosis	
n	xx
Mean	x.x
SD	x.x
1 st Quartile	x.x
Median	x.x
3 rd Quartile	x.x
IQR	x.x
Min, Max	x.x,x.x
Undocumented BMI	xx
Insurance Category, n (%)	
Sub-total	xxx
Private Insurance Only	n (x.x%)
Public Insurance Only	n (x.x%)
Both Public and Private Insurance	n (x.x%)
Other	n (x.x%)
Unknown/Undocumented	n (x.x%)
Region of Residence, n (%)	
Sub-total	xxx
West	n (x.x%)
Midwest	n (x.x%)
Northeast	n (x.x%)
South	n (x.x%)
Undocumented Region	n (x.x%)

## 7.1.2. Clinical Characteristics

**Table 2. Clinical Characteristics**

	N=xxx
Classification of Disease at Initial AML Diagnosis, n (%)	
Sub-total	xxx
AML with Recurrent Genetic Abnormalities	n (x.x%)
AML with Multi-lineage Dysplasia	n (x.x%)
Therapy-Related Myeloid Neoplasm	n (x.x%)
Myeloid Proliferations Related to Down Syndrome	n (x.x%)
Myeloid Sarcoma	n (x.x%)
Undifferentiated or Biphenotypic Acute Leukemias	n (x.x%)
Other Classification AML	n (x.x%)
Undocumented AML Classification	n (x.x%)
AML Type, n (%)	
Sub-total	n (x.x%)
DeNovo	n (x.x%)
Secondary	n (x.x%)
Hypomethylating Agents before initial AML treatment	n (x.x%)
Undocumented	n (x.x%)
Performance Status at Initial AML Diagnosis (ECOG Score), n (%)	
Sub-total	n (x.x%)
0	n (x.x%)
1	n (x.x%)
2	n (x.x%)
3	n (x.x%)
4	n (x.x%)
Undocumented ECOG	n (x.x%)
Composite Performance Status at Initial AML Diagnosis, n (%)	
Sub-total	n (x.x%)
Impaired	n (x.x%)
No Documentation of Impairment	n (x.x%)
Cytogenetic/FISH Testing at Initial AML Diagnosis,** n (%)	
t(6;9)(p23;q34.1)	
Yes	n (x.x%)
No	n (x.x%)
Undocumented	n (x.x%)
t(6;9)(p23;q34.1) Positive Test Results (yes), n (% out of Patients Tested)	
t(v;11q23.3)	
Yes	n (x.x%)
No	n (x.x%)
Undocumented	n (x.x%)
t(v;11q23.3) Positive Test Results (yes), n (% out of Patients Tested)	
t(9;22)(q34.1;q11.2)	
Yes	n (x.x%)

**Table 2. Clinical Characteristics**

	N=xxx
No	n (x.x%)
Undocumented	n (x.x%)
t(9;22)(q34.1;q11.2) Positive Test Results (yes), n (% out of Patients Tested)	n (x.x%)
inv(3)(q21.3q26.2) or t(3;3)(q21.3;q26.2)	
Yes	n (x.x%)
No	n (x.x%)
Undocumented	n (x.x%)
inv(3)(q21.3q26.2) or t(3;3)(q21.3;q26.2) Positive Test Results (yes), n (% out of Patients Tested)	n (x.x%)
-5 or del(5q); -7; -17/abn(17p)	
Yes	n (x.x%)
No	n (x.x%)
Undocumented	n (x.x%)
-5 or del(5q); -7; -17/abn(17p) Positive Test Results (yes), n (% out of Patients Tested)	n (x.x%)
Complex karyotype	
Yes	n (x.x%)
No	n (x.x%)
Undocumented	n (x.x%)
Complex karotype Positive Test Results (yes), n (% out of Patients Tested)	n (x.x%)
Monosomal karyotype	
Yes	n (x.x%)
No	n (x.x%)
Undocumented	n (x.x%)
Monosomal karotype Positive Test Results (yes), n (% out of Patients Tested)	n (x.x%)
t(8;21)(q22;q22.1)	
Yes	n (x.x%)
No	n (x.x%)
Undocumented	n (x.x%)
t(8;21)(q22;q22.1) Positive Test Results (yes), n (% out of Patients Tested)	n (x.x%)
inv(16)(p13.1q22) or t(16;16)(p13.1;q22)	
Yes	n (x.x%)
No	n (x.x%)
Undocumented	n (x.x%)
inv(16)(p13.1q22) or t(16;16)(p13.1;q22) Positive Test Results (yes), n (% out of Patients Tested)	n (x.x%)

**Table 2. Clinical Characteristics**

	N=xxx
Biomarker Testing at Initial AML Diagnosis,* n (%)	
FLT3	
Yes	n (x.x%)
No	n (x.x%)
Undocumented	n (x.x%)
FLT3 Positive Test Results (yes), n (% out of Patients Tested)	n (x.x%)
IDH1	
Yes	n (x.x%)
No	n (x.x%)
Undocumented	n (x.x%)
IDH1 Positive Test Results (yes), n (% out of Patients Tested)	n (x.x%)
IDH2	
Yes	n (x.x%)
No	n (x.x%)
Undocumented	n (x.x%)
IDH2 Positive Test Results (yes), n (% out of Patients Tested)	n (x.x%)
TP53	
Yes	n (x.x%)
No	n (x.x%)
Undocumented	n (x.x%)
TP53 Positive Test Results (yes), n (% out of Patients Tested)	n (x.x%)
NPM1	
Yes	n (x.x%)
No	n (x.x%)
Undocumented	n (x.x%)
NPM1 Positive Test Results (yes), n (% out of Patients Tested)	n (x.x%)
Provider Documentation of ELN Genetic Risk Stratification, n (%)	
Favorable	n (x.x%)
Intermediate	n (x.x%)
Adverse	n (x.x%)
Undocumented	n (x.x%)
ELN Genetic Risk Stratification Based on Biomarker Testing, n (%)	
Favorable	n (x.x%)
Intermediate	n (x.x%)
Adverse	n (x.x%)
Undocumented	n (x.x%)
Comorbidities, n (%)	
HIV+/AIDS	n (x.x%)

**Table 2. Clinical Characteristics**

	N=xxx
Alzheimer's or Other Dementia	n (x.x%)
Cerebrovascular Accident	n (x.x%)
Chronic Obstructive Pulmonary Disease	n (x.x%)
Cirrhosis or Other Serious Liver Disease	n (x.x%)
Congestive Heart Failure	n (x.x%)
Connective Tissue Disease	n (x.x%)
Diabetes	n (x.x%)
Hemiplegia	n (x.x%)
Leukemia (other than AML)	n (x.x%)
Metastatic Solid Tumor	n (x.x%)
Myocardial Infarction	n (x.x%)
Peripheral Vascular Disease (History of Surgical Treatment For)	n (x.x%)
Renal Disease	n (x.x%)
Ulcer Disease	n (x.x%)
Weighted Index of Comorbid Conditions*	
Mean	x.x
SD	x.x
1 st Quartile	x.x
Median	x.x
3 rd Quartile	x.x
IQR	x.x
Min, Max	x.x,x.x
Subsequent Treatment,± n (%)	n (x.x%)

\*This is a weighted index of comorbid disease condition. Weighting of comorbid conditions will follow the weighting as specified in the Charlson Comorbidity Index.

\*\*If multiple tests have been performed, the test that was closest to the index date (initial diagnosis of AML) would be presented.

± Any treatment received after the first R/R-based line of therapy.

1. Indicative of favorable risk according to 2017 ELN guidelines.
2. Indicative of intermediate risk according to 2017 ELN guidelines.
3. Indicative of adverse risk according to 2017 ELN guidelines.
4. Because of missing data or undocumented testing, misclassification bias may be present.

